The main foreseeable risk factor here is missing data. As abdominal USS scans will be performed in clinical radiology departments and many factors out of our control may impact on timing and scheduling, missing scans or scans performed outside of timing windows may occur. In order to mitigate this we will ensure that there is clear communication between the local research coordinators/nurses and the clinical team about timing and windows, and in parallel we will ensure that the lead PI will communicate regularly with site PIs to maintain engagement and encouragement with regard to adherence to study protocols and timing. There is a risk that scans may not capture all requisite elements we are planning to collect data on. We will mitigate this by ensuring clear lines of communication between local PIs and their radiology colleagues, and clear written communication from the RECOVER team to radiology departments in relation to the vital role they play in the study, and the importance of collecting data as outlined on the study sheets. We will regularly feedback to the local teams and radiology departments in relation to study progress in an effort to maintain engagement and active participation.

Some individuals may be reluctant or unable to give stool specimens at the nominated times. Study nurses/coordinators will work closely with subjects to encourage/remind them in relation to timelines and facilitate collection of specimens as much as possible. We expect that an incomplete set of stool samples will be collected and have factored this into our study calculations in terms of numbers and budget. With a recruitment of 201 individuals we would ideally expect 772 stool samples. In reality we estimate that it is likely that we will have 85% of individuals produce one sample, 80% to produce 2 samples and 70% to produce 3 samples and 60% to produce 4. This is outlined in table 9.

Visit	0	1	6	24	Total
Numbers	156	117	131	113	517

Table 9. Estimated total number of stool samples

Specific Aim 5 for Parent Study and Extension Study – Liver Manifestations

P.I. [name]

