The aim of the CF liver disease arm of RECOVER is to gain a greater understanding of the changes in CF liver manifestations in people on CFTR modulator therapy. This is done by analyzing data from liver ultrasounds, liver function tests and other blood tests. For the parent study, LFTs are monitored every 3 months for the first year and at year two. Liver exams and ultrasounds will be carried out at baseline, year one and year two. For the extension study, LFTs are monitored annually as part of normal clinical care. Ultrasounds will be performed where indicated as part of normal clinical care at the participating center (most RECOVER sites perform annual ultrasound screening).

Liver Examination for the Parent Study

As part of the formal assessment of classification of CFLD (CFLD, non-specific [NSCFLD] and No LD), site investigators at all sites will be asked to clarify specifically on physical examination whether there is a hard liver and splenic enlargement at study baseline and at year one and two. Specific guidance will be provided around clinical examination via a training video by the lead hepatologist (BB) on the study. The baseline liver disease status of participants in the Republic of Ireland will be updated/confirmed using data from the Irish longitudinal study on cystic fibrosis liver disease study (ILSCFLD) based on previously collected data. The data from examination, ultrasound and blood tests will be collated on the CFLD worksheet (figure 7). A single paediatric (BB) and a single adult (AM) hepatologist will review the worksheets together in batches after each assessment window and determine which group subjects should be allocated to. If there is a discrepancy between ILSCFLD allocation and RECOVER baseline allocation these will be reviewed as a group by the study hepatologists and a confirmed allocation agreed to enable longitudinal assessment using ILSCFLD data.

CFLD V	Vorkshe	eet Now	el Modulato	r Therapy C	tcomes with ombinations rstic Fibrosis	REC	Øv	P.I. Pau
Study Code		Study visit			Age at asses	ssment		
Clinical exami	nation							
Was clinical e	xamination per	formed?	YES	NO				
Was there a h	ard liver edge?	?	YES	NO				
Was the splee	en abnormally l	arge	YES	NO				
Liver Ultrasou	ind							
Did the subje	ct have a Liver	USS?	YES	NO				
Abnormal ech	otexture		YES	NO				
Nodules			YES	NO				
Spleen size (c	m)				Integer with	one decimal		
Portal Flow			NOR	MAL	IMPAIRED	REVERSE		
Liver function	tests/other							

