AST	Normal	1-2xULN	2-3xl	JLN	3-5xULN	>5xULN		
ALT	Normal	1-2xULN	2-3xl	JLN	3-5xULN	>5xULN		
ALP	Normal	1-2xULN	2-3xl	JLN	3-5xULN	>5xULN		
GGT	Normal	1-2xULN	2-3xl	JLN	3-5xULN	>5xULN		
PLT		Integer						
РТ		Integer						

Figure 7. RECOVER CFLD worksheet for the Parent Study.

Liver Function Test

Liver function test results (AST, ALT, GGT, ALP, Bilirubin, albumin) will be collected from medical notes prior to drug initiation, 3 monthly for the first year for the parent study and annually thereafter for the remainder of the parent study and the extension study (this is a mirror of the requirements put in place by the health service for sites in ROI when all previous CFTR modulator therapies were introduced). For UK sites LFTs results will be collected from medical notes in accordance to required schedule of collection based on drug approval and funding. The following data from annual labs will be entered into the eCRF: Hemoglobin, hematocrit, platelets, white cell count, prothrombin time. The mean levels, and incidence of elevations of AST or ALT to greater than specified multiple (1-2xULN, 2-3xULN, 3-5xULN and >5xULN) times the upper limit of normal will be compared between those on ETI and (1) their liver function tests in the 2 years prior to starting ETI and (2) age matched historic (modulator naïve) controls from within the last 5 years.

P.I. [name]

Ultrasound

As per routine clinical practice in most centers, people with CF from 6 years of age onwards will have annual liver ultrasound scans as part of annual assessment. In centers where this is not the case, ultrasound scans will be performed for the purposes of the study. Ultrasound scans will be performed using a proforma schedule for reporting the findings including liver texture, the presence of nodules and liver edge irregularity and spleen size with reported measurement of AP length (figure 5). The presence of abnormal liver echotexture, evidence of retrograde portal venous flow and spleen size will be compared between those on ETI and (1) their liver ultrasounds, where available, in the 2 years prior to starting ETI and (2) age matched historic CF (modulator naïve) controls from within the last 5 years (Irish sites).

End of parent study assessment

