Eligibility Assessment	Х	Х															
Sweat Chloride		Х				Х		Х				Х	Х	х	Х	х	Х
LCI	Х	Х				Х		Х		Х		Х	Х	Х	Х	Х	Х
Spirometry-controlled CT (A*)		Х						Х				Х		X1		X1	
Height/Weight/BMI*	Х	Х			Х	Х	Х	Х	Х	Х	Х	Х	Х	Х	Х	Х	Х
FEV1*	Х	Х			х	Х	Х	х	Х	Х	Х	Х	Х	х	х	Х	Х
Airway Sampling (Micro)*	Х	Х			Х	Х	Х	Х	Х	Х	Х	Х	Х	Х	Х	Х	Х
Nasal Lavage (A*)		Х				Х		Х				Х	Х	х	х	Х	Х
FeNO	Х	Х				Х		Х									
Liver Function Testing*		Х			Х	Х	Х	Х				Х	Х	х	Х	Х	Х
Liver Ultrasound		Х						Х				Х	Х	Х	Х	Х	Х
Sputum Collection (A*)		Х				Х		Х		Х		Х	Х	х	Х	Х	Х
Liver Examination		Х						Х				Х					
Stool Collection		Х	Х			Х						Х	Х	х	Х	Х	Х
Blood Collection		Х						Х				Х	Х	Х	Х	Х	Х
Breath Sample Collection		Х			Х	Х	Х	Х									
Abdominal Symptom Score	Х	Х	Х	Х		Х		Х				Х	Х	х	Х	Х	Х
CFQ-R		Х				Х		Х				Х	Х	Х	Х	Х	Х
Pharmacy Records MPR								Х				Х					
Adherence Questionnaire	Х	Х			Х	Х	Х	Х	Х	Х	Х	Х					
MEMs Caps Reading (M)								Х				Х					
Antibiotic Use		Х						Х				Х					
Adverse Event Check			Х	Х	Х	Х	Х	Х	Х	Х	Х	Х	Х	Х	Х	Х	Х
Mental Health Questionnaire													Х	Х	Х	Х	Х

* Collected as normal clinical care,

A - Advanced arm testing in RECOVER parent study

¹ Only for patients who performed spirometry-controlled CT in parent study. Scan at years four and six at sites doing routine clinical CT. Scan at year six for sites not performing biennial CT

M - MEMs study only

Table 14. Schedule of assessments. Each visit has a study window. For the RECOVER parent study the baseline visit (0 month visit) will have an 8 week pre commencement on ETI start window. The 1, 2 and 3 month visits have +/- 2 week window. The 6, 9, 12, 15, 18, 21 and 24 month visits have +/- 1 month window. For the RECOVER extension study each annual visit will have a window of +/- 4 month.

Study Governance and Management Plan

RECOVER

[figure not shown]

Figure 6 RECOVER study management structure.

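### The liver ultrasound comparison does not single out the month-0 proforma scan, so differences in reporting or in who has earlier scans could mimic or mask change on ETI

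*Protocol*

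**What the plan says.** In the protocol's Ultrasound subsection (Specific Aim 5, Liver Manifestations), study scans follow a fixed form: "Ultrasound scans will be performed using a proforma schedule for reporting the findings including liver texture", with nodules, edge irregularity and spleen size also listed. The planned analysis reads: "The presence of abnormal liver echotexture, evidence of retrograde portal venous flow and spleen size will be compared between those on ETI". Two comparators follow. The first is "their liver ultrasounds, where available, in the 2 years prior to starting ETI". The second is age-matched, modulator-naïve historic controls from the last five years at Irish sites. The subsection does not say how either set of scans was reported, whether they will be re-read, how several earlier scans from one person are combined, or whether the comparison is paired.

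Elsewhere the protocol provides a pre-treatment study scan. The introduction to Specific Aim 5 states: "Liver exams and ultrasounds will be carried out at baseline, year one and year two". The note to Table 14 says that "the baseline visit (0 month visit) will have an 8 week pre commencement on ETI start window". Under Subjects on ETI, people already taking the drug may be recruited in exceptional circumstances if baseline data exist from clinical care or approved research.

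**The concern.** A before/after comparison of reported findings is interpretable only if the findings are looked for and recorded in the same way on both sides. A proforma prompts for each item; a routine report need not mention an item at all. The background section on CF liver disease presents structured ultrasound reporting as something this study contributes, so it is fair to infer that some earlier reports were less structured. If silence in such a report is read as absence, abnormality already present before ETI is counted as new on ETI.

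The qualification about availability adds a second problem, because the people who have earlier scans may not be like those who do not. At stake is one secondary outcome, but the protocol's preliminary results section says that the study will test whether CFTR modulation improves indices of CF liver disease, and these ultrasound features are among them.

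**Working it through.** **No plan figure to reproduce.** The protocol gives no rate, effect size or power for liver ultrasound. What follows is an illustration.

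**Inputs**
- p, true prevalence of the abnormality, unchanged by ETI: 10% to 30%, assumed. The upper value has a loose anchor in the Irish liver cohort in the preliminary results: 335 without liver disease, 110 non-specific, 35 with CF liver disease, so (110 + 35)/480 = 30.2%. That is any liver abnormality, not echotexture specifically, and it says nothing about retrograde portal flow.
- s, the share of abnormalities that earlier reports record: assumed. The proforma is taken to record all of them, which is generous to the proforma.
- a1 and a0, the shares of abnormal and normal participants who have an earlier scan: assumed.

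**Step 1: reporting difference alone, earlier scans for everyone.** Apparent rise = p × (1 − s).

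| | s = 1.0 | s = 0.8 | s = 0.7 |
|---|---|---|---|
| p = 10% | 0 | 2 points | 3 points |
| p = 20% | 0 | 4 points | 6 points |
| p = 30% | 0 | 6 points | 9 points |

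With 201 per side (a sample size used in the protocol's power tables), unpaired and two-sided at 5%, the chance of a false significant difference at p = 30% is about 27% for s = 0.8 and 54% for s = 0.7.

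**Step 2: add selective availability.** If all on-ETI scans are set against whichever earlier scans exist, earlier recorded prevalence = p × a1 × s / [p × a1 + (1 − p) × a0]. With p = 30%, a1 = 90%, a0 = 60%, the denominator is 0.27 + 0.42 = 0.69.
- s = 1.0: 0.270/0.69 = 39.1%, difference 30 − 39.1 = −9.1 points
- s = 0.8: 0.216/0.69 = 31.3%, difference −1.3 points
- s = 0.7: 0.189/0.69 = 27.4%, difference +2.6 points

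With a0 = 45% the difference at s = 0.7 is 30 − 0.189/0.585 × 100 = −2.3 points. The sign therefore depends on inputs the documents do not give.

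**Step 3: pairing.** If only people with an earlier scan were compared with themselves, selection would no longer reverse the sign. The s = 0.7 case (a0 = 60%) becomes 39.1 − 27.4 = +11.7 points, in a group richer in liver disease. The subsection does not fix pairing, and the historic-control comparison cannot be paired within person.

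**Step 4: month-0 proforma scan as comparator.** Same form and same people on both sides makes s equal before and after, so the reporting-format artefact is 0 points for any p.

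**The case against.** The strongest reply is that the sound comparator is already there. The month-0 scan is scheduled, falls within eight weeks before ETI, and so lies inside the two-year window. That stands for anyone enrolled before treatment. What remains is that the subsection does not single this scan out and pools it with earlier scans of unstated format.

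A reader might infer that fuller reporting will make ETI appear to cause liver abnormality. The documents do not support that. They do not say how earlier or control scans were reported, and Step 2 shows the bias can run the other way. Nor does the argument cover spleen size, which is a measurement.

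A reader might also take the remark under Risks with GI Data Collection, "There is a risk that scans may not capture all requisite elements we are planning to collect data on", as evidence that earlier reports are incomplete. It concerns the study's own scans and, if anything, narrows the gap. Nor do centres without routine scanning lose their pre-ETI scan: the protocol has ultrasounds done there for the study, so those participants lack only earlier scans.

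Two further points carry some weight. Specific Aim 5 also compares liver disease groups before and after ETI, from worksheets reviewed by the same two hepatologists; that is a separate analysis and does not repair this one. Item coding is often left to an analysis plan, and the protocol does allow imputation with complete-case checks, but those handle an unmentioned item properly only if it is coded as missing in the first place.

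**Conclusion.** The point holds as a weakness in how the comparator is specified, not as a demonstrated bias towards harm. Proforma-reported scans on ETI are set against earlier and control scans with no requirement of common reporting, and the one like-for-like scan is not named. For echotexture and portal flow, a reporting difference could mimic or mask change; differences in who has earlier scans could do the same, in either direction. The illustrative range at 30% prevalence, from −9.1 to +9 points in Steps 1 and 2, rests wholly on assumed reporting and availability rates, and its prevalence anchor does not extend to retrograde flow. The exposure is greatest for the historic controls, for earlier clinical scans, and for participants recruited already on ETI whose baseline came from clinical care. This is a cheap improvement to one secondary outcome.

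**What to change.** In the Ultrasound subsection, name the month-0 proforma scan as the main within-person comparator for echotexture, portal flow and spleen size at months 12 and 24. Present three other comparisons as supportive, with the difference in reporting stated: earlier routine scans, historic controls, and the clinical-care baselines of participants recruited already on ETI. State that an item not mentioned in a routine report is coded as missing, not absent.

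The cost is wording only, since the scan is already scheduled. The downside is that participants without a month-0 proforma scan leave the main comparison. For spleen size, the change gives a common form and a recent reference but does not remove the effect of growth in children. Re-reading stored earlier and control images on the proforma, blind to ETI status, would strengthen the supportive comparisons where feasible, but the main change does not depend on it.

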The prevalence of CFLD ranges from 10–30%, depending on the criteria used to define liver disease(41-43). Currently there are two very similar consensus approaches to define CFLD(35, 44) which classify PWCF into three groups (i) CFLD; includes those with clinical evidence of liver disease (with or without portal hypertension), histological evidence on liver biopsy or radiological evidence of portal hypertension (ii) NSCFLD includes those with non-specific ultrasound or biochemical evidence of liver disease who do not fulfill criteria for CFLD, and (iii) those with no evidence of liver disease. When a diagnosis is established there are no clinical indicators that predict disease progression. More importantly, there is no effective intervention for prevention or treatment of established disease until liver transplantation for end-stage liver failure(35, 37).

In clinical trials, CFTR modulator drugs have been shown to be associated with elevation of liver transaminases, at times leading to cessation of treatment, temporarily in most instances. Little is understood about this or the natural history of variations in transaminases in CF. The medium to long term implications of

P.I. [name]

alterations of transaminases with CFTR modulator therapy is also unclear. Weight gain in individuals on lvacaftor is significant, and predominantly related to fat mass(45), raising concerns about the development of hepatic steatosis, although a single reported case has demonstrated the opposite, an improvement in steatosis on commencement of lvacaftor(46). A structured approach to the reporting of ultrasound findings such as in this study will shed light on this.

CFTR Modulators

Ivacaftor, the first mainstream CFTR modulator (a potentiator) is licenced for use in children with CF aged one year and older with a gating mutation and leads to improvements in sweat chloride, pulmonary function, weight gain, quality of life and rate of decline in lung function (47-51). Interestingly, in children aged 1 to 5 years, Ivacaftor was associated with improvements in markers of pancreatic insufficiency on treatment (52). Ivacaftor is currently in clinical trials in infants from birth to one year, and if found to be safe, will be the first disease modifying treatment available to infants with CF from birth.

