At the end of the parent study, the liver disease status of participants (CFLD, non-specific [NSCFLD] and No LD) will be updated based on study assessments and review of study worksheets. Proportions of subjects in each group will be compared before and after modulator therapy in addition to determining how many individuals from each given group move to another group on ETI. This will be compared to historic natural history data from the ILSCFLD study for ROI participants.

Classification as part of extension study

Classification will be assigned to each participant as having CFLD, NSCFLD or NoLD annually during the extension study as above.

Specific Aim 6 for Parent Study and Extension Study – Pulmonary Exacerbations and Antibiotic Use

IV Antibiotic Therapy

The number of courses of IV antibiotics (hospitalizations and home IVs) and their indication (elective or unplanned) will be recorded over the duration of the study. This data will be collected in conjunction with clinical staff at local sites. The number (and number of days) of IV antibiotic courses over the length of the study timeframe will be compared with the number of IV antibiotic courses (and days) in the five years prior to commencement of ETI. Some individuals will have started on previous generations of CFTR modulators in the two to three years prior to the initiation of ETI, in which case data will be available for IV antibiotic courses before and on previous CFTR modulator therapy as well as on ETI.

Oral Antibiotic Use

The number of courses, total number of days and type of oral antibiotics will be collected from pharmacy records submitted with parent/guardian consent (and ethical approval) at the end of the study period as part of the adherence arm of RECOVER. The number of courses and number of days of oral antibiotic use will be documented in the eCRF. Given the complexity of the system at UK sites for collection of this information, data on oral antibiotic use from community pharmacies will be collected only from sites in Ireland.

Analysis of Data

Given the depth of information collected through RECOVER we will be in a position to compare antibiotic use to pulmonary outcome measures such as lung function, structure and inflammation, and non-pulmonary indices such as sweat chloride and medication adherence.

Definition of Exacerbation

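### The before/after liver-class comparison can count an on-ETI transaminase rise with no ultrasound or examination change as a move from no liver disease to NSCFLD

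*Protocol*

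**What the plan says.** The three classes are defined once, in the Background under CF Liver Disease. There, "NSCFLD includes those with non-specific ultrasound or biochemical evidence of liver disease who do not fulfill criteria for CFLD". The word "or" makes biochemical evidence sufficient by itself. CFLD needs clinical evidence of liver disease, histology, or radiological evidence of portal hypertension.

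The same section states that "CFTR modulator drugs have been shown to be associated with elevation of liver transaminases". It adds: "Little is understood about this or the natural history of variations in transaminases in CF", and calls the medium- to long-term implications unclear.

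Under Specific Aim 5 (Liver Examination for the Parent Study), examination, ultrasound and blood results go onto the worksheet in Figure 7. It carries AST, ALT, ALP and GGT in multiples of the upper limit of normal, plus platelets and prothrombin time. One paediatric and one adult hepatologist "will review the worksheets together in batches after each assessment window and determine which group subjects should be allocated to".

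End of parent study assessment then fixes the comparison: "Proportions of subjects in each group will be compared before and after modulator therapy", together with a count of those who change class. "This will be compared to historic natural history data from the ILSCFLD study for ROI participants".

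Separately, the Liver Function Test and Ultrasound subsections compare AST/ALT levels and elevations, and ultrasound findings, with each participant's preceding two years and with modulator-naive historic controls.

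**The concern.** The class is a composite of structural and laboratory evidence, and the protocol itself says drugs of this type act on part of the laboratory evidence. When such a composite is compared before and after starting the drug, a shift across the NoLD/NSCFLD boundary has two possible explanations: a change in liver disease, or a laboratory effect of treatment whose meaning the protocol calls poorly understood. The planned summary does not tell them apart. Equal numbers of blood tests before and after would not help, because the issue is what the test reflects and not how often it is done.

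The ILSCFLD comparison does not remove the ambiguity. Its follow-up ran from 2007 to 2017, and the protocol dates European approval of ETI to 2020. That natural history therefore contains no ETI laboratory effect to cancel against.

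At stake is how the class result bears on the hypothesis that ETI improves liver outcomes. An excess of NoLD-to-NSCFLD moves could be read as progression when no ultrasound or examination finding had changed. If transaminases fell on balance, moves in the other direction could be read as improvement on equally weak grounds.

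**Working it through.** **1. Does the text permit the move?**
- Definition (Background, CF Liver Disease): ultrasound or biochemical evidence suffices for NSCFLD.
- Drug effect (same section): modulators are associated with raised transaminases.
- Inputs to the class (Figure 7): AST, ALT, ALP and GGT bands, the first abnormal band being 1 to 2 times the upper limit of normal.
- Rule for on-treatment rises: none is stated. The worksheet has no field for attribution or persistence.
- Link between the separate ultrasound and liver-test comparisons and the transitions: none is stated.

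A participant with unchanged ultrasound and examination and a raised ALT on ETI can therefore be placed in NSCFLD. The same participant cannot reach CFLD by this route.

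**2. Reproducing the natural-history figure (Preliminary Results, CF Liver Disease).** 119/335 = 35.5%, as printed, and 13/335 = 3.88%, as printed. The sentence gives the NoLD group once as 355, but 119/355 = 33.5%, so the printed percentages use 335.

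**3. Two-year equivalent.** Assuming a constant hazard over ten years:
- 1 − (1 − 119/335)^(2/10) = 1 − 0.6448^0.2 = 0.084, or 8.4%.
- A straight-line share gives 35.5%/5 = 7.1%.

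**4. Illustration of size.** The protocol gives no rate of drug-related rise. Let x be the share of NoLD participants who have a drug-only rise at the classifying visit and are placed in NSCFLD because of it, independently of natural movement. Apparent movement = 1 − (1 − 0.084)(1 − x).

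| x (assumed) | Apparent two-year movement | Ratio to 8.4% |
|---|---|---|
| 5% | 1 − 0.916 × 0.95 = 13.0% | 1.5 |
| 10% | 1 − 0.916 × 0.90 = 17.6% | 2.1 |
| 15% | 1 − 0.916 × 0.85 = 22.1% | 2.6 |

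In head-counts, assume the ILSCFLD class mix (335 NoLD, 110 NSCFLD, 35 CFLD, so 335/480 = 69.8% NoLD). At the cap of 254 there would be about 177 NoLD participants and 177 × 0.084 ≈ 15 natural movers. The extra movers would be 177 × 0.916 × x ≈ 8, 16 and 24. The ILSCFLD comparison covers Republic of Ireland participants only, so its counts would be smaller.

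**5. Sensitivity to the natural rate.** The 119 participants showed nonspecific evidence at the 2017 follow-up. That is a state at one time point, not a count of irreversible onsets. If people move in and out of NSCFLD, two-year movement could be well above 8.4%. At the extreme of 35.5%:
- x = 5%: 1 − 0.645 × 0.95 = 38.7%, ratio 1.09
- x = 10%: 1 − 0.645 × 0.90 = 42.0%, ratio 1.18
- x = 15%: 1 − 0.645 × 0.85 = 45.2%, ratio 1.27

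The ratio therefore depends heavily on an assumption that the protocol cannot settle.

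**The case against.** A reader might infer that the plan automatically counts every ALT rise on ETI as new CF liver disease and so biases Aim 5 towards harm by a factor of 1.5 to 2.6. The documents do not support that, for these reasons:

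- **The class is adjudicated.** Two hepatologists decide it from the whole worksheet and can discount a rise they think is drug-related. This stands, so the move can be counted but need not be. Informal discounting would not settle the matter: the class could then follow different rules before and on treatment, and different rules from ILSCFLD.
- **NSCFLD is not CFLD.** By definition it covers people who do not meet CFLD criteria. This stands; only the NoLD/NSCFLD boundary is exposed.
- **Components are already analysed.** Ultrasound findings and AST/ALT elevations have their own comparisons, and the list of secondary outcomes names liver function testing and ultrasound but not the three-level class. A structural benefit would thus not be invisible. Neither comparison, however, is tied to the transitions set against ILSCFLD.
- **Details may sit elsewhere.** The definition summarises cited consensus approaches, and thresholds or persistence rules may be in those sources or in a statistical analysis plan that is not at hand. This is fair, and it limits how firmly the problem can be asserted. The protocol nonetheless fixes both the comparison and the inputs to the class.
- **Net direction is unknown.** No rate or duration of ETI-related rises is given. A rise that resolves before the year-one or year-two assessment need not appear. Aim 6 notes that some participants took earlier modulators before ETI, so their baseline may already carry the effect. This stands.

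**Conclusion.** The concern holds in limited form. As written, the three-class before/after and transition comparison can mix a drug-related laboratory change with a change in liver disease at the NoLD/NSCFLD boundary, and nothing in the protocol requires the two to be separated. The ILSCFLD natural history cannot separate them either.

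Neither the size nor the net direction can be derived from the document. The rise from 8.4% to between 13% and 22% is an illustration. It rests on an assumed 5% to 15% drug-only rise, a constant hazard, independence of the two routes, and no discounting by the hepatologists. With fluctuating NSCFLD status the ratio could fall to between about 1.1 and 1.3. This is a cheap improvement to interpretability; it does not show that the liver aim is invalid.

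**What to change.** In End of parent study assessment, keep the three-class comparison and add that every transition, in either direction, is reported as one of two kinds:

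1. supported by a change on ultrasound or examination;
2. biochemistry only.

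Base any statement about progression or improvement of liver disease on kind 1, including the comparison with ILSCFLD where its component data allow the same split. Report kind 2 as an on-ETI laboratory outcome beside the planned AST/ALT analysis. Because the split covers both directions, it guards against apparent improvement as well as apparent harm.

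For RECOVER the cost is a change of wording and one derived variable, since the components are already on the Figure 7 worksheet. For ILSCFLD it is more: that cohort collected clinical, biochemical and radiological assessments, but the protocol does not divide the 119 movers by type of evidence, so the split would have to be derived there. The statistical price is fewer events in kind 1 and hence less precision. Keeping the three-class result alongside preserves comparability with published ILSCFLD classes.
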